2.3.2 Known potential benefits

There are no direct established health benefits from the DE-CBCT. However, the subjects' participation in this study will provide essential data that could potentially improve health outcomes, that would eventually benefit the society at large.

2.3.3 Risk-benefit assessment

Although participants do not benefit directly from the DE-CBCT scan, the additional risks are minimal. The device design, intended to deliver low doses for maxillofacial imaging, is the key method to minimize current risks, as well as risks to patients for potential future use.

3 OBJECTIVES AND ENDPOINTS

3.1 Primary objective

To evaluate the effectiveness and safety of DE-CBCT to assess jaw bone density and compare these values with MDCT, an established standard for assessment of BD.

3.2 Secondary objective

To analyze the agreement between the BD assessments by the evaluators

4 STUDY DESIGN

4.1 Overall design

This study will test the hypotheses that DE-CBCT will be equivalent to MDCT to assess BD in the jaw bones.

The study design is an open-label clinical trial to evaluate the effectiveness and accuracy of DE-CBCT to assess BD in jaw bones. This single center trial will enroll 24 subjects, with equal gender distribution. In order to investigate the HU values of bone density across the intended patient population age range, the patients will be recruited according to the three classified age groups. Each study subject will receive both the investigational DE-CBCT and the standard of care MDCT scan, which serves as the control.

Age Group	Number of Patients
Below age 45 (≤ 45 years old)	Male : 4 Female: 4
Older than 45 and less than 65 (45 – 65 years old)	Male : 4 Female: 4
Over age 65 (≥ 65 years old)	Male : 4 Female: 4

The study-specific procedures will be completed in two visits at the UCLA Dental Center and the UCLA Ronald Reagan Hospital. Subjects recruited into the study are those requiring CT imaging for dental diagnosis or treatment planning, including but not limited to implant treatment planning, jaw bone pathoses, impacted teeth etc. In order to mark the ROI area, the dental surgeon will fabricate a custom acrylic stent worn by the patient during imaging. The stent incorporates radiopaque markers that indicate the location(s) and angulation(s) of the proposed ROI area.

The study-specific procedures are as below:

Screening	Informed consent	Study-specific process, 20-30 min
Visit 1	DE-CBCT (experimental scan)	~20 min

Visit 2	MDCT (Standard of care scan)	~20 min
---------	------------------------------	---------

Following scan acquisition, the study's investigators will evaluate the CT scan and make BD assessments at specific locations, as directed by the radiopaque markers in the stent. BD will be assessed in at least three individual sites per subject.

4.2 *Scientific rationale*

The basic premise of this study is that the investigational device (DE-CBCT) will provide accurate estimates of BD in the dento-alveolar bone. The accuracy of DE-CBCT assessments will be determined against the clinical gold standard for BD assessment. The outcome of this study will demonstrate the efficacy and accuracy of DE-CBCT to assess BD at jaw sites.

4.3 *Blinding*

Evaluators are able to distinguish DE-CBCT and MDCT by appearance and thus cannot be blinded to the modality. However, investigators measuring the BMD will be blinded to the measurements on the standard/experimental CT, and to measurements made by other investigators, until the measurement phase is completed. The statistician will remain blinded, until the data is locked and delivered for statistical analysis.

4.4 *Justification for dose*

Not applicable

4.5 *End of study definition*

A participant will be considered to have completed the study if he/she has completed both scheduled visits including the DE-CBCT and MDCT imaging.

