DURATION OF SUBJECT PARTICIPATION AND DURATION OF STUDY	
Subjects will be on study for up to 30 days
 
Total Study period: 12 months
 
Enrollment & Follow-up: 1 month
 
The total duration of the study is expected to 12 months. Once enrolled, the test subject will be on the study for one month including recruitment and final subject follow-up.

STUDY METHOD	
The study is based on two visits (VISIT 1 and VISIT 2)
 
 • DAY 0 (enrollment): Subject is queried for inclusion/exclusion criteria and informed about the study. If he/she agrees to participate, inclusion/exclusion criteria and informed consent will be documented. An imaging stent, which bears radiopaque markers, will be also created for each patient. • VISIT 1: Inclusion/exclusion criteria will be reconfirmed and the DE-CBCT imaging will be completed. • VISIT 2 (no more than 30 days since the enrollment): Inclusion/exclusion criteria will be reconfirmed and MDCT imaging completed. 
- Depending on availability of scheduling on MDCT unit, Visit 2 may occur on the same day as Visit 1.

Clinical Assessments	
The following assessments will be performed and recorded on Case Report Form:
 
 • Demographics • Any relevant medical history • Site-specific BD assessment (Region of Interest, ROI) • Adverse Events
PRIMARY ENDPOINT	Jaw BD (HU values) assessed by DE-CBCT and by MDCT
SECONDARY ENDPOINT	Agreement between the BD assessments by evaluators

SAFETY EVALUATIONS	Incidence of adverse events (AE): Adverse events on the days of the study visits will be documented. The PI/staff evaluates the severity of AE and the causal relationship using 'safety evaluation criteria.' The PI will report the case to the investigator/sponsor and IRB subsequently.
PLANNED INTERIM ANALYSES	None
STATISTICS Primary Analysis Plan	
 The correlation between DE-CBCT and MDCT HU values of bone density will be performed using Pearson. The agreement between DE-CBCT and MDCT HU values of bone density will be performed using Bland-Altman plots. In order to evaluate the observer reliability, Kappa statistics will be performed.

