5 STUDY POPULATION

5.1 *Rationale for Number of Subjects*

Based on the reference paper called "Bone quality evaluation at dental implant site using multislice CT, micro-CT, and cone beam CT," the correlation coefficient of human mandibular bone density (HU) between CBCT and MDCT was observed to be 0.89. In assumption that there also exists a correlation between the HU values of DE-CBCT images and MDCT images, Pearson's correlation analysis was considered for calculating the appropriate number of patients for the current study.

With 0.05 Type 1 Error (significance level 5%) and 80% statistical power, the number of patients is calculated to be 7. Further considering the three age groups and 10% of dropout rate will result in a total of 24 patients to be enrolled in the study.

Below is the hypothesis and calculation formula:

- Hypothesis:

Null hypothesis : $H_0 : \rho = 0$, Alternative hypothesis : $H_1 : \rho = r_0 \neq 0$

- Formula:

$$n = \left(\frac{z_{\alpha/2} + z_{\beta}}{C(r_0)} \right)^2 + 3, \quad C(r_0) = \frac{1}{2} \ln \left(\frac{1+r_0}{1-r_0} \right)$$

In : Log to the base of e

r_0 : Correlation coefficient value to be tested

α : Type 1 error

β : Type II error

$z_{\alpha/2}$: Value corresponding to $100(\alpha/2)\%$ in the standard normal distribution curve

z_{β} : Value corresponding to $100(\beta)\%$ in the standard normal distribution curve

- Calculation:

$$\textcircled{1} \quad \alpha=0.05, 1-\beta=0.80$$

$$\textcircled{2} \quad r_0=0.89$$

$$\begin{aligned} n &= \left(\frac{z_{\alpha/2} + z_{\beta}}{C(r_0)} \right)^2 + 3, \quad C(r_0) = \frac{1}{2} \ln \left(\frac{1+r_0}{1-r_0} \right) \\ &= \left(\frac{1.960 + 0.842}{1.422} \right)^2 + 3 = 6.88 \end{aligned}$$

$$\textcircled{3} \quad \text{Three age groups: } 7 \times 3 = 21$$

$$\textcircled{4} \quad \text{Dropout rate: 10\%, n=24}$$

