8.2 Efficacy assessments

BD Assessment

In each patient's MDCT and DE-CBCT scans, discrete regions of interest (ROIs) will be made in the area where radiographic imaging is necessary for the dental diagnosis and treatment plan. The ROI will be angulated, sized, and positioned to mark the treatment area. Using the software tools, the BD will be assessed and recorded. The assessments at each location will be recorded and the HU values of DE-CBCT will be correlated with those of MDCT.

Assessments will be made independently by two oral and maxillofacial radiologists. Each radiologist will make these assessments twice, with at least one month between the two assessments.

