9 STATISTICAL CONSIDERATIONS

In this study, we seek to recruit 24 patients to evaluate the effectiveness and safety of DE-CBCT for assessing jaw bone density compared to the current clinical gold standard for BD measurement, MDCT. This primary objective will be analyzed by correlating DE-CBCT HU values to MDCT HU values and Pearson will be performed for the correlation. The higher the correlation coefficient, the more DE-CBCT correlated to MDCT, meaning DE-CBCT is equivalent to the clinical use of MDCT.

To evaluate the accuracy of DE-CBCT and its equivalence to MDCT, we will analyze the agreement between the two methods using Bland-Altman plots.

To evaluate the intra- and inter-observer reliability, observer we will use Kappa statistics to:

1. Quantify the level of agreement between duplicate assessments by the same radiologist
2. Quantify the level of agreement between independent assessments by the two radiologists

Evaluation analysis group

In this clinical trial, the data from PP analysis group (Per-Protocol Analysis Set) will be analyzed.

① Per Protocol Analysis Set:

The PP analysis group includes subjects who complete the study according to the study plan without a significant violation of the protocol- from voluntarily agreeing to participate in the study to finishing the scanning of both DE-CBCT and MDCT. If the quality of image is affected by the metal prosthesis, the subject corresponding to the image is excluded from the PP analysis group.

② A major violation of the study plan to be excluded from the PP analysis group:

The quality of the image, especially the area where ROI is located, is degraded by the metal prosthesis.

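### At least three sites per patient go into Pearson and Bland-Altman with no unit of analysis or clustering rule; pooled as independent pairs, they would overstate precision

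*Combined protocol and SAP*

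**What the plan says.** Section 4.1 sets the measurement plan: "BD will be assessed in at least three individual sites per subject". All of a patient's sites come from one DE-CBCT scan and one MDCT scan. Section 8.2 continues: "The assessments at each location will be recorded and the HU values of DE-CBCT will be correlated with those of MDCT". Section 4.2 gives the aim at the same level: "The outcome of this study will demonstrate the efficacy and accuracy of DE-CBCT to assess BD at jaw sites".

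On readings, Section 8.2 has two radiologists working independently, and "Each radiologist will make these assessments twice, with at least one month between the two assessments". That is four readings per site and modality.

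On analysis, the synopsis (Section 1.1) says "The correlation between DE-CBCT and MDCT HU values of bone density will be performed using Pearson", and Section 9 says "we will analyze the agreement between the two methods using Bland-Altman plots". Section 9 uses the repeat readings only for kappa, for example to "Quantify the level of agreement between duplicate assessments by the same radiologist". The sample size in Section 5.1 counts patients: "the number of patients is calculated to be 7", then three age groups and dropout bring the total to 24.

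No section states the unit of analysis, averages sites within a patient, names a method for clustered data, or says how the four readings become the HU value that enters the comparison.

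**The concern.** The sections on measurement and aim point to site-level pairs, while the sample size is built on patients. Ordinary Pearson inference and the usual Bland-Altman intervals assume independent pairs. Sites in one patient share two scans, and under Section 8.1 usually one jaw, since either the mandible or the maxilla is imaged. Section 8.1 also selects the imaging mode by patient size and field of view. Any scan-level or patient-level shift in HU moves all of that patient's sites together, so three sites carry less information than three independent patients.

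What is at stake is the stated precision of r, of the mean bias and of the limits of agreement. Section 4.1 hypothesises equivalence and Section 9 argues it from r and the Bland-Altman plot. With about 21 to 24 patients, a reader needs an honest interval to judge that claim.

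Two further gaps follow from the same silence. A minimum of three sites, with no maximum, lets patients with more sites weigh more. And the analyst could choose among sites, patient means or individual readings after seeing the data.

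**Working it through.** **Inputs from the protocol.** At least 3 sites per patient (Section 4.1); 2 radiologists x 2 readings (Section 8.2); two-sided alpha 0.05, power 80%, r0 = 0.89, null rho = 0, three age groups, 10% dropout, 24 patients (Section 5.1).

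**Assumed, because the documents do not give it.** A within-patient correlation (ICC): of HU values for inference on r, and of DE-CBCT minus MDCT differences for bias and limits. The main range is 0.3 to 0.7, with lower values shown. Also assumed: 21 evaluable patients, exactly three sites each, normal data.

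**The plan's own figure.** C(0.89) = 1.422, so n = ((1.960 + 0.842)/1.422)² + 3 = 6.88, rounded up to 7. Then 7 x 3 = 21 and 21 x 1.1 = 23.1, rounded up to 24. This reproduces, and it treats each patient as one independent pair.

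**Mean bias, by formula.** With m = 3 sites, pooling understates the variance of the mean difference by the factor 1 + (m − 1) x ICC. At ICC 0.3/0.5/0.7 this is 1.6/2.0/2.4. The true standard error is therefore 1.26/1.41/1.55 times the naive one, and 63 pooled sites are worth 63/1.6 = 39, 63/2.0 = 32 and 63/2.4 = 26 independent pairs.

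**Test of rho = 0, by formula.** The approximate factor is 1 + (m − 1) x ICC² = 1.18/1.50/1.98 when both modalities share the ICC.

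**Simulation of naive pooling (21 patients x 3 sites, 40,000 runs).**

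| ICC | True size of nominal 5% test of rho = 0 | Coverage, r at 0.89 | Coverage, mean bias | Coverage, one limit of agreement |
|---|---|---|---|---|
| 0 | 5.1% | about 95% | about 95% | about 95% |
| 0.1 | 5.3% | 94.8% | 92.9% | 93.8% |
| 0.2 | 6.0% | 94.3% | 90.3% | 92.7% |
| 0.3 | 7.0% | 92.9% | 87.9% | 90.8% |
| 0.5 | 11.0% | 88.9% | 83.1% | 86.6% |
| 0.7 | 16.9% | 83.3% | 78.9% | 81.7% |

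With 24 patients instead of 21, the results at ICC 0.3/0.5/0.7 are nearly the same: size 7.2/10.9/16.8%; coverage 93.0/89.4/83.6% for r, 87.8/83.3/79.0% for bias and 91.0/86.8/81.7% for a limit.

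**What this does to the interval for r.** The Fisher-z interval is tanh(atanh(0.89) ± 1.96/√(n − 3)).
- 63 sites taken as independent: 1.422 ± 0.253, giving 0.824 to 0.932.
- All sites kept, patients left out one at a time (jackknife on Fisher z, t with 20 df): median interval 0.814 to 0.938 at ICC 0.3, 0.802 to 0.943 at 0.5, and 0.781 to 0.949 at 0.7.
- One value per patient, n = 21: 1.422 ± 0.462, giving 0.744 to 0.955. This also reflects the loss of site-level information, so the whole difference from the first line is not clustering error.

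**What hardly moves.** The expected pooled variance of the differences is 1 − 2 x ICC/62 of its true value, so the SD is 0.995/0.992/0.988 of the truth at ICC 0.3/0.5/0.7. At r = 0.89 with 21 patients, t = 0.89 x √(19/(1 − 0.7921)) = 8.5 on 19 df, so p is about 7 x 10⁻⁸.

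**Readings.** Three sites x 2 radiologists x 2 readings give 12 readings per modality per patient. Entering all of them as separate pairs would be worse than pooling sites, by an amount that depends on reading error. The documents give no reading error, so no figure is claimed.

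**The case against.** The strongest reply is that no section says sites will be pooled. Recording values at each location can be read as data capture, and a sample size in patients fits one pair per patient equally well. Strictly, the documents show an omission, and the coverage losses follow only under one reading of it. That stands, and the conclusion is conditional for that reason. The site-level reading is still the natural one, and the plan names no patient-level summary.

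Next, the plan lists no interval for r, bias or limits, and its only formal hypothesis, rho = 0, would be rejected at the planned r under any approach. The plotted limits barely move. All true, and these points cap the severity. They do not remove the need for a sound measure of precision in a study this small that argues equivalence.

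Finally, the range 0.3 to 0.7 has no source in the documents, and the correlation of differences may be lower than that of HU values. Section 2.2 reports that conventional CBCT numbers vary with anatomical location, which could make differences vary within a patient. That is fair: at 0.1 the losses are slight, as the table shows. Nothing in the plan establishes that the correlation is that low.

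**Conclusion.** The concern holds and should be fixed. The plan collects clustered data, names methods that assume independence, and does not state the unit of analysis or how readings are combined. If sites are pooled, nominal 95% intervals cover about 88% to 79% for mean bias, 91% to 82% for a limit of agreement and 93% to 83% for r at 0.89, and the 5% test of rho = 0 has a true size of about 7% to 17%. These figures rest on 21 patients, three sites each, normal data and an assumed within-patient correlation of 0.3 to 0.7; at zero correlation there is no distortion. The effect of unequal site numbers was not quantified. The omission itself is certain; the size of the harm depends on the correlation and on the analyst's choice.

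**What to change.** In Section 9:

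1. State that the patient is the independent unit.
2. Combine the four readings into one HU value per site and modality by a stated rule, for example the mean, and keep the separate readings for the reliability analysis.
3. Use Bland-Altman for multiple observations per individual, or a mixed model of the DE-CBCT minus MDCT difference with a random patient effect.
4. Obtain intervals for r, bias and limits by leaving out or resampling whole patients.
5. Add a sensitivity analysis on patient means.

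For r, the leave-one-patient-out jackknife on Fisher z with n − 1 degrees of freedom is a workable choice. In simulation at ICC 0.3/0.5/0.7 it covered 94.9/94.8/94.8%, with type I error 4.9/5.2/5.4%. A percentile bootstrap of 21 patients covered only about 92%. A t interval on patient means covered about 95% for bias.

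The cost is a few sentences and slightly more programming, with no change to patients, scans or visits. Reported intervals become wider, and with 21 patients jackknife intervals for the limits still cover slightly under nominal, about 92% to 93%.

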5 STUDY POPULATION

5.1 *Rationale for Number of Subjects*

Based on the reference paper called "Bone quality evaluation at dental implant site using multislice CT, micro-CT, and cone beam CT," the correlation coefficient of human mandibular bone density (HU) between CBCT and MDCT was observed to be 0.89. In assumption that there also exists a correlation between the HU values of DE-CBCT images and MDCT images, Pearson's correlation analysis was considered for calculating the appropriate number of patients for the current study.

With 0.05 Type 1 Error (significance level 5%) and 80% statistical power, the number of patients is calculated to be 7. Further considering the three age groups and 10% of dropout rate will result in a total of 24 patients to be enrolled in the study.

Below is the hypothesis and calculation formula:

- Hypothesis:

Null hypothesis : $H_0 : \rho = 0$, Alternative hypothesis : $H_1 : \rho = r_0 \neq 0$

- Formula:

$$n = \left(\frac{z_{\alpha/2} + z_{\beta}}{C(r_0)} \right)^2 + 3, \quad C(r_0) = \frac{1}{2} \ln \left(\frac{1+r_0}{1-r_0} \right)$$

In : Log to the base of e

r_0 : Correlation coefficient value to be tested

α : Type 1 error

β : Type II error

$z_{\alpha/2}$: Value corresponding to $100(\alpha/2)\%$ in the standard normal distribution curve

z_{β} : Value corresponding to $100(\beta)\%$ in the standard normal distribution curve

- Calculation:

$$\textcircled{1} \quad \alpha=0.05, 1-\beta=0.80$$

$$\textcircled{2} \quad r_0=0.89$$

$$\begin{aligned} n &= \left(\frac{z_{\alpha/2} + z_{\beta}}{C(r_0)} \right)^2 + 3, \quad C(r_0) = \frac{1}{2} \ln \left(\frac{1+r_0}{1-r_0} \right) \\ &= \left(\frac{1.960 + 0.842}{1.422} \right)^2 + 3 = 6.88 \end{aligned}$$

$$\textcircled{3} \quad \text{Three age groups: } 7 \times 3 = 21$$

$$\textcircled{4} \quad \text{Dropout rate: 10\%, n=24}$$

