Rationale for Number of Subjects	
The correlation coefficient of human mandibular bone density (in HU) between CBCT and MDCT was observed to be 0.89, according to the study conducted by Parsa et al. (Reference paper: Bone quality evaluation at dental implant site using multidetector CT, micro-CT, and cone beam CT)
 
Using the formula below, the number of patients is calculated to be 7.
 $n = \left(\frac{z_{\alpha/2} + z_{\beta}}{C(r_0)} \right)^2 + 3, \quad C(r_0) = \frac{1}{2} \ln \left(\frac{1 + r_0}{1 - r_0} \right)$ 
Since we have three age groups (7x3 = 21) and expect the dropout rate to be 10% (21x(1+0.1)=24), a total of 24 patients will be enrolled for the current study.

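### The 80% power in Section 5.1 is for rejecting zero correlation in one age group, not for the equivalence hypothesis of Section 4.1, and Section 9 lets a high r be read as equivalence

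*Combined protocol and SAP*

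**What the plan says.** Section 4.1 sets the hypothesis: "This study will test the hypotheses that DE-CBCT will be equivalent to MDCT to assess BD in the jaw bones". It recruits in three age groups of eight, with the stated aim "In order to investigate the HU values of bone density across the intended patient population age range", and adds: "BD will be assessed in at least three individual sites per subject".

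Section 5.1 bases the sample size on Pearson's coefficient: "correlation analysis was considered for calculating the appropriate number of patients for the current study". Its null hypothesis is rho = 0, and its alternative is a non-zero rho, set at 0.89 from a published comparison of CBCT with MDCT. It continues: "With 0.05 Type 1 Error (significance level 5%) and 80% statistical power, the number of patients is calculated to be 7". Then: "Further considering the three age groups and 10% of dropout rate will result in a total of 24 patients to be enrolled in the study". The Section 1.1 synopsis repeats the formula and the steps 7, 21 and 24, without the 80%.

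Section 9 has two statements about equivalence. One says that a larger Pearson coefficient means that DE-CBCT can be taken as equivalent to MDCT in clinical use. The other assigns accuracy and equivalence to Bland-Altman plots. Neither comes with a margin, limits of acceptable agreement or a success rule. Section 8.2 has two radiologists each reading every location twice.

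**The concern.** The hypothesis that is powered and the hypothesis that the trial says it tests are different. Rejecting rho = 0 shows that the two sets of HU values are linearly related to some degree. It does not show that they agree.

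The protocol's own background explains why this matters. Section 2.2 says that conventional CBCT numbers already relate linearly to object density, yet converting them to HU has not worked. A strong linear relation without HU agreement is therefore the very problem the device is meant to solve, and Pearson's r cannot detect it.

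At stake is the reported conclusion. As Section 9 stands, a high r could be presented as equivalence, with an 80% power figure apparently behind it, even if the Bland-Altman plot showed a material bias.

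**Working it through.** **1. Reproduce the plan's figure.** Inputs from Section 5.1: two-sided alpha 0.05 (z = 1.960), power 80% (z = 0.842), r0 = 0.89.

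- C(0.89) = ½ ln(1.89/0.11) = 1.422
- n = ((1.960 + 0.842)/1.422)² + 3 = 6.88, rounded up to 7
- 7 × 3 = 21; 21 × 1.1 = 23.1, rounded up to 24

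All steps match the document.

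**2. What the 80% refers to.** Power to reject rho = 0 at rho = 0.89 is approximately Φ(1.422·√(n − 3) − 1.960), with one value per patient.

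- n = 7: Φ(2.844 − 1.960) = 81% (88% when the t-test of r is simulated)
- n = 21: Φ(6.033 − 1.960), over 99.9% (the simulation agrees)

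So 80% belongs to one age group of 7. A pooled test of rho = 0 in 21 patients is close to certain to reject.

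**3. How little is needed to reject rho = 0.** The smallest r significant at two-sided 5% is t/√(t² + n − 2): 0.75 at n = 7 and 0.43 at n = 21. A pooled r of 0.43 would reject the Section 5.1 null hypothesis.

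**4. Why r cannot carry equivalence.** For any constant a and any b > 0, corr(x, a + b·y) = corr(x, y). Illustration with an assumed proportional under-reading: a site at 1000 HU is class D2 (850–1250) in the Misch table of Section 2.2. It drops below 850 HU once the under-reading exceeds 1 − 850/1000 = 15%, and it stays in D3 (350–850) up to 65%. At 30% it reads 700 HU. Throughout this range r is unchanged.

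**5. Precision of the Bland-Altman bias (indicative only).** The documents do not say how several sites and four readings per site enter the analysis. Assume 21 patients, 3 sites each, readings averaged within site, and an intraclass correlation (ICC) of the site differences within patient. The design effect is 1 + 2·ICC, and the 95% half-width is t(20)·√((1 + 2·ICC)/63), in SDs of the site-level difference.

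| ICC | Effective pairs | Half-width (SD) |
|---|---|---|
| 0 | 63 | 0.26 |
| 0.25 | 42 | 0.32 |
| 0.5 | 31.5 | 0.37 |
| 0.75 | 25.2 | 0.42 |
| 1 | 21 | 0.46 |

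Treating 63 pairs as independent gives t(62)/√63 = 0.25 SD. Treating all 21 × 3 × 4 = 252 readings as independent gives about 0.12 SD, which understates the uncertainty further.

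**The case against.** The strongest defence is that Section 9 does not rest on r alone. It assigns Bland-Altman plots to accuracy and equivalence, and the synopsis lists correlation and agreement as separate analyses. This stands: a reader might infer that bias would go unseen, and the documents do not support that. What it does not answer is that the plots have no acceptance limits, played no part in the sample size, and come with no rule for the case where plot and correlation disagree.

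Second, Section 5.1 states its null hypothesis openly and computes it correctly. This also stands. A reader might infer that 24 patients are too few, but the documents give no acceptable HU difference and no SD of the paired differences, so that cannot be shown. With 21 patients, one value each, an assumed true difference of zero and two one-sided 5% tests, power is 43%, 78%, 91% or 99% for assumed margins of 0.5, 0.65, 0.75 or 1.0 SD of the difference. The answer depends entirely on a margin that has not been set.

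Third, Section 8.1 calibrates DE-CBCT on a hydroxyapatite phantom and scans a calibration phantom alongside MDCT. This makes a large bias less likely without excluding it. The 30% figure is an illustration, not a forecast, and the Misch classes are background, not an endpoint.

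Fourth, because age groups tripled the sample and Section 9 names no age-group analysis, a reader might infer that the age results will be left out. Section 9 is only silent, and recruiting by age can serve simply to cover the age range.

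**Conclusion.** The point holds. The stated hypothesis is equivalence; the stated 80% power is for rejecting rho = 0 with 7 patients in one age group. The Section 9 sentence that turns a higher r into equivalence is wrong as written, because r ignores constant and proportional bias. This follows from the text and from a property of r, and needs no assumption.

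The defect lies in the inference and the wording. It is not an arithmetic error, and it is not a demonstrated shortage of patients. The figure of over 99.9% for a pooled test assumes one value per patient. The half-widths of 0.26 to 0.46 SD assume 21 patients, 3 sites, averaged readings and an unknown ICC. The ratio of 0.46 to 0.25, about 1.8, should not be taken as a ceiling on how far a naive interval could be too narrow, since each site is read four times and Section 4.1 allows more than three sites.

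**What to change.** Keep 24 patients and change the following.

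1. **Section 9.** Replace the sentence linking a higher r to equivalence with: *Pearson's r describes linear association only and will not be used to conclude equivalence. Agreement will be judged from the Bland-Altman mean bias and limits of agreement, with 95% CIs.*
2. **Sections 5.1 and 1.1.** State that the 7 per age group, at 80% power, is for rejecting rho = 0 only, and that no power for equivalence is claimed.
3. **Section 4.1.** Unless the sponsor prespecifies an acceptable HU difference before data lock, reword the hypothesis as estimating the agreement between DE-CBCT and MDCT, and make no formal equivalence claim. Without this step, the first two changes would leave a promised equivalence test with no criterion.
4. **Section 9, confidence intervals.** Take the patient as the independent unit. Average the repeat readings per site, then use patient means with t(n − 1) for the bias and a repeated-measures variance-components method for the limits of agreement. Avoid an uncorrected percentile bootstrap of patients. In simulation with 21 patients, 3 sites, normal differences and ICC 0.25 to 0.75 (all assumed), its nominal 95% intervals covered about 92 to 93% for the bias and 87 to 89% for the upper limit of agreement.
5. **Optional.** Report the bias descriptively by age group, after making the Section 4.1 groups non-overlapping; ages 45 and 65 each now fall in two groups.

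The cost is wording in four sections and, if wanted, one descriptive table. No extra patients, scans or readings are needed. The downside is a less favourable power statement, wider intervals than naive ones, and no equivalence claim from r.
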